Study Design: This aim of the study will be a multi-site clinical trial conducted at Mayo Clinic, University of Minnesota (UMN), and Georgia Tech (GT). Mayo Clinic will serve as the Reviewing IRB, and UMN, UTMB, and GT, will be relying institutions. We will be assessing the effectiveness of the Sensoria® Mat and AW-Shift© systems (seat mat and mobile app) for changing the movement behavior of wheelchair users at risk for pressure injuries. Two different types of feedback (from the Sensoria® Mat and AW-Shift© respectively) will be provided separately, through the use of a cross-over design.

A longitudinal, within subject, cross-over study design will be implemented. Changes in movement behavior will be compared between baseline and two intervention phases (AW-Shift© and Sensoria® Mat). A third system, the Wheelchair In-Seat Activity Tracker (WiSAT) will collect movement data passively in the background throughout the duration of the entire study period. This system is being used for collecting the movement data only and is not part of the study interventions. Each permutation of the two interventions will be tested across two groupings, with 30 participants in each (Figure 2). Participants will be in the active study intervention phases for a total of 8 weeks and overall study participation will last about 13 weeks. If one of the phases of the study needs to be paused or delayed (due to equipment delays/malfunctions, participants/study staff scheduling, etc.), the duration of the study may be longer than 13 weeks, but will be no longer than 21 weeks. Participants will not be actively participating in the study during equipment repair downtime.

[figure not shown]

Figure 2. Aim 3 full clinical trial study design. Groups are arranged horizontally. Green arrows are pre-intervention calls and red arrows are post-intervention calls.

Due to unforeseen issues with equipment and anticipated enrollment/financial timeline constraints, we will update our study design to allow a limited number of participants to complete only one of the intervention periods if necessary. We will alternately choose either the AW-Shift© or Sensoria® for up to 20 participants at each study site (Mayo and GT). The timeline for these participants is shown in Figure 3. **This abbreviated study design will not apply retrospectively to participants already enrolled in the full-length study. Once**

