Target accrual: We plan to accrue a total of 60 adult individuals who use a manual or power wheelchair for their primary form of mobility may be at risk for pressure injuries. Enrollment will be split between the Mayo Clinic (n=30) and GT (n=30) sites.

Subject population: Participants will be recruited from the Mayo Clinic Spinal Cord Injury Registry (IRB #16-001004), the electronic medical record (EPIC), clinician/staff referrals, other related studies, and from previous aims of this project (IRB #s: 17-007956, 18-009718). Recruitment methods may include email, letter, flyer, social media, business card, and phone call.

Inclusion Criteria: Potential eligible subjects must:

1. Currently be age 18 years or older;
2. Be able to come to the Mayo Clinic, UMN, or GT campuses for study visits, or participate in virtual (video) study visits;
3. Qualify for or use a skin protection or skin protection and positioning wheelchair cushion;
4. Be able to perform weight-shifts independently without assistance of another person (by moving themselves or using of power tilt);
5. Own and be able to operate a smartphone with Apple or Android operating system; and
6. Are willing to download and use the mobile app on their phone.

Exclusion Criteria: Subjects will be excluded if:

1. They are scheduled for flap surgery;
2. There is an active stage 3, 4, or unstageable pressure injury as defined by the National Pressure Injury Advisory Panel definitions anywhere on their sitting surface at time of enrollment;
3. They use a custom molded or alternating air wheelchair cushion;
4. Have/use the recline function on manual or power wheelchair;
5. They have a prescribed or limited sitting time of less than 5 hours per day;
6. They live in a long-term care facility or group home and require 24 hours/day assistance; or
7. They have a known history of any condition or factor judged by the investigator to preclude participation in the study or which might hinder adherence.

Research Activity

Check all that apply and complete the appropriate sections as instructed.

1. **Tests & Procedures:** Collection of data through noninvasive tests and procedures routinely employed in clinical practice that may include: MRI, surface EEG, echo, ultrasound, moderate exercise, muscular strength & flexibility testing, biometrics, cognition testing, eye exam, etc. (Specify in the Methods section)

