Secondary: The secondary endpoint will be the change in self-efficacy between baseline and interventions.

Tertiary: The tertiary endpoint will be the difference in effectiveness between systems (interventions).

Power Statement: This aim is powered based on the primary outcome measure of in-seat movement behavior, quantified as the change in weight-shifts per hour from baseline to during the use of an intervention. A clinically meaningful change in movement (~50% increase) was defined by preliminary data from the WiSAT system. The data will be analyzed using a mixed effect model with fixed effects for treatment and time trend, and mixed effects for subject and time trend within subject. Power calculations were estimated via simulation. Various scenarios defined by sample size, effect sizes and variances (for error and random effects) were inspected by creating 1000 simulated data sets for each scenario. The response was assumed to be log-normally distributed, with log-transformations employed for modeling. Power was estimated using the percentage of simulated data sets returning a significant result for the hypothesis of interest. All tests are 2-sided with a 0.05 Type I error rate. Table 1 shows the results using a standard deviation of 0.35 (for the log-response), and 0.8 and 0.2 for the random effects of subject and time-subject. Forty-eight subjects will achieve 97% power to detect a 50% increase in weight-shifts and 100% power to detect a 100% increase regardless of sample size (Table 1), as well as sufficient power to detect differences between the 2 interventions (Table 1). Sample size below 48 participants does not allow for sufficient power to detect intervention vs. intervention differences. To accommodate 20% attrition, a total of 60 participants will be recruited into the study.

Sample Size	Intervention vs Baseline			Intervention vs Intervention		
	25% ↑	50% ↑	100% ↑	0% vs 50%	25% vs 50%	50% vs 100%
48	55%	97%	>99%	>99%	67%	96%
54	61%	98%	>99%	>99%	71%	97%
60	66%	99%	>99%	>99%	78%	98%

Table 1. Statistical power at 0.05 significance level for varying sample sizes at standard deviation (error)=0.35

Data Analysis Plan: Interim monitoring and early stopping rules are documented in the Data Safety and Monitoring Plan. The statistician will be masked to the intervention type during data analysis. All tests are 2-sided with a 0.05 Type I error rate. Analysis will be conducted with SAS and R software.

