Covariates/Confounding Variables: For all outcome measures, the effect of **relevant biological variables** including **sex, age**, and pressure injury history will be assessed as covariates in the analysis. Additionally, wheelchair type and level of sensation will be included in the covariate space. Randomization will be blocked by site to reduce any confounding effects of study site. Variables will be transformed as necessary to meet appropriate distributional assumptions for modeling (e.g. normality).

SA3a Hypothesis: Individuals will complete more frequent and more consistent weight-shifts with access to the feedback systems compared to baseline: The change in-seat movement frequency (weight-shifts/hour) and consistency (max and COV of time between weight-shifts) between baseline and interventions will be analyzed using a mixed effect model with fixed effects for treatment and time trend, and mixed effects for subject and time trend within subject. Movement during the washout periods will be adjusted for in the analysis if during washout, the participants do not return back to their baseline movement level.

SA3b Hypothesis: Self-efficacy beliefs for completing weight-shifts will increase with use of the feedback systems: The change in self-efficacy will be analyzed using a mixed effect model as described in SA3a Hyp.

Other Outcome Measures: The difference in effectiveness between systems (interventions) will be analyzed using a mixed effect model as described in SA3a Hyp. The QUEST and SWLS questionnaire and mobile app interaction results will be analyzed using repeated measures ANOVA to determine if there are differences across intervention phases.

Missing Outcome Data: The primary outcome measure is collected passively with no need for the participant to interact with the system (no battery charging needed during this phase). The questionnaires are collected via phone/video call, so we are not relying on returned paper copies. Mixed models handle missing data naturally, so that all available data points may be analyzed, irrespective of whether the subject had some outcome data missing. However, analyses of data with multiple imputation for missing data may be attempted, if the data are likely to be missing at random.

References

1. Krause, J.S., *Skin sores after spinal cord injury: Relationship to life adjustment*. Spinal Cord, 1998. **36**(1): p. 51-6.

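### The power statement and Table 1 ignore the abbreviated pathway, which can put up to 40 of 60 participants on one system only, so the stated between-system power is not assured

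*Combined protocol and SAP*

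**What the plan says.** The Study Design section plans a cross-over in which participants use both systems, 30 in each order. It then adds an amendment to "allow a limited number of participants to complete only one of the intervention periods if necessary", with one system chosen alternately for "up to 20 participants at each study site (Mayo and GT"). The rule looks forward only: "This abbreviated study design will not apply retrospectively to participants already enrolled in the full-length study".

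Target accrual is unchanged: "We plan to accrue a total of 60 adult individuals", 30 at each of the two sites.

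The Power Statement claims 97% power for a 50% increase over baseline with 48 subjects, "as well as sufficient power to detect differences between the 2 interventions (Table 1"). It adds "Sample size below 48 participants does not allow for sufficient power to detect intervention vs. intervention differences", and reaches 60 from 48 by allowing for 20% attrition. Table 1 gives between-system power at 48 of >99% (0% v 50%), 67% (25% v 50%) and 96% (50% v 100%). The abbreviated pathway appears nowhere in this section.

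The between-system comparison is still planned. Endpoints says "The tertiary endpoint will be the difference in effectiveness between systems (interventions"), while Secondary Outcome Measures lists it as secondary. Under Missing Outcome Data, the mixed model is to be fitted so that "all available data points may be analyzed".

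**The concern.** Table 1 appears to describe participants who all use both systems, since that design reproduces its figures. The amended design no longer guarantees that. At the ceiling only 60 − 40 = 20 participants use both systems before attrition, against a stated minimum of 48 for this comparison.

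There is also no slack. After the planned attrition 60 × 0.8 = 48, exactly the stated minimum, so if attrition runs as planned every abbreviated participant pulls between-system power below the tabulated value.

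What is at stake is how a non-significant difference between systems would be read. A reader who trusts 96% power may take it as evidence that the systems perform alike, when the design actually run may have had clearly less.

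Separately, the claim of sufficient between-system power carries no qualification, yet Table 1's 25% v 50% column shows 67%, 71% and 78%. All three are below the conventional 80%, a standard the plan does not itself state.

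**Working it through.** **Inputs from the Power Statement.** Two-sided 0.05; log-scale error SD 0.35; random subject SD 0.8; random time-within-subject SD 0.2; fixed effects for treatment and time trend. Effects on the log scale: 25% v 50% is ln(1.5/1.25) = 0.182; 50% v 100% is ln(2/1.5) = 0.288; a 50% rise over baseline is ln(1.5) = 0.405.

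**Assumptions, because the documents are silent.** One value per phase; abbreviated participants contribute baseline plus one phase, split equally between systems; attrition falls equally on both pathways; phase times (0, 0.6, 1.6). The times were chosen to fit Table 1, so the match below is calibration, not independent confirmation.

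**Method.** Generalised least squares standard error (SE) for the stated model, then power ≈ Φ(δ/SE − 1.96).

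**Step 1: reproduce Table 1 at 48 participants using both systems.** SE is 0.107 against baseline and 0.076 between systems.

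| Contrast | Stated | Recomputed |
|---|---|---|
| 25% rise v baseline | 55% | 55% |
| 50% rise v baseline | 97% | 97% |
| 25% v 50% | 67% | 67% |
| 50% v 100% | 96% | 97% |

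**Step 2: change the mix.** Between-system power by number abbreviated out of 60:

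| Abbreviated of 60 | 25% v 50%, all analysed | 50% v 100%, all analysed | 25% v 50%, 20% attrition | 50% v 100%, 20% attrition |
|---|---|---|---|---|
| 10 | 71% | 98% | 62% | 95% |
| 16 | 68% | 97% | 58% | 93% |
| 20 | 65% | 96% | 56% | 91% |
| 30 | 58% | 93% | 49% | 86% |
| 40 | 50% | 87% | 41% | 79% |

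At the ceiling the between-system SE is 0.094 for 20 full + 40 abbreviated, and 0.105 for 16 + 32 after attrition.

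**Step 3: hand check of the ceiling.** A participant using both systems gives a within-person difference with variance 2(0.35²) + 0.2²(1.6 − 0.6)² = 0.285, so 20 of them give precision 20/0.285 = 70.2. An abbreviated participant's change from baseline has variance 2(0.35²) + 0.2²(0.6²) = 0.259. Comparing 20 with 20 gives variance 2 × 0.259/20 = 0.0259, or precision 38.6. The total is 108.8, so SE = 1/√108.8 = 0.096. Power is Φ(0.182/0.096 − 1.96), about 47%, and Φ(0.288/0.096 − 1.96), about 85%. The full model does slightly better because it weights the baseline optimally. Per person, an abbreviated participant carries about (38.6/40)/(70.2/20) = 27% of the between-system information of a full-length one.

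**Step 4: sensitivity.**
- Five other time codings, (0, 0.5, 1.5), (0, 0.75, 2), (0, 0.75, 2.25), (0, 1, 2) and (0, 1, 3): together with the main coding, 44-50% and 82-87% at 20 + 40, and 37-42% and 73-79% at 16 + 32. Codings (0, 0.75, 2.25) and (0, 1, 3) already understate Table 1 for 25% v 50% at 48 (63% and 60%).
- Adding a washout value at baseline level gives 54% and 90% at 20 + 40, and 45% and 83% at 16 + 32. That variant gives 91% where Table 1 has 55% for a 25% rise over baseline, so it checks only the between-system loss.
- 0% v 50% stays at about 94% or more in every variant tried.

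**Step 5: primary contrast, 50% rise, stated 97%.** At the ceiling it is about 94-97% with all 60 analysed and 87-93% after attrition, under codings that give 97-98% at 48. Coding (0, 1, 2) is left out of this step because it gives 88% at 48 and so does not match Table 1.

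**The case against.** The strongest reply is that little of consequence changes. Forty is a ceiling on an optional, forward-looking pathway. It can be reached only if no more than 10 of 30 per site had already enrolled full-length, and the documents do not give that number. With 16 to 20 abbreviated and everyone analysed, the tabulated figures at 48 are about kept. The aim is powered on change from baseline, and the between-system comparison ranks lower. Against an 80% yardstick, the same cells pass and fail at the ceiling without attrition as in Table 1: 50% v 100% passes and 25% v 50% fails. Deleting dropouts entirely is also pessimistic, because a full-length participant who leaves after phase 1 still contributes. Finally, Table 1 prints the 67% openly.

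Most of this is fair, and it limits the size of the problem. It does not remove it. The plan's own attrition allowance turns 60 into 48, so counting dropouts as lost follows its convention; keeping phase-1 data for the four full-length dropouts at the ceiling moves 50% v 100% only from 78.5% to 80.3%. All the figures above already credit abbreviated participants' data. The Power Statement still presents a figure for a design that no longer has to be the one run. The division 48/0.8 = 60 is correct; the fault is a basis that was not updated.

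**Conclusion.** The concern holds and should be fixed. The 40-of-60 ceiling and the absence of the pathway from the Power Statement are plain from the text. The percentages are of moderate certainty, since they rest on one value per phase, a time coding fitted to Table 1, equal allocation of abbreviated participants and equal attrition.

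On that basis the stated between-system power is not assured, and at the permitted maximum it is not met. The loss is roughly 17 to 26 percentage points for 25% v 50% and 9 to 17 for 50% v 100%, without and with attrition respectively. Large differences (0% v 50%) remain detectable, and the effect on the primary contrast is modest.

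**What to change.** Rerun the existing simulation under the planned model for the expected mix and for the maximum mix (20 full + 40 abbreviated enrolled; 16 + 32 after 20% attrition), each with and without attrition. State the time coding, the observations per phase and how washout data enter. Report those results for the primary contrast in place of the lone 97%, which can stay only if labelled as the case where all 48 use both systems. Replace the unqualified claim of sufficient between-system power, and restate the 48-participant minimum as numbers completing both phases plus numbers completing one.

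Suggested text: *Up to 40 of 60 participants may complete one intervention phase only. Power for the expected and the maximum mix, with and without 20% attrition, is [results]. The design can detect between-system differences of [x] and cannot reliably detect differences of [y].*

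The cost is a rerun of existing code and a few sentences. No participants or procedures are added. The only downside is a less favourable stated power.

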Initial/Baseline Visit: This visit may be completed in-person, or virtually. The subject will receive standard guidelines/education on weight-shift frequency for pressure injury prevention, and may have their skin health reviewed by the study team. Research staff will provide a basic overview of all systems and mobile apps. The WiSAT mat will be installed underneath the participant's wheelchair cushion to monitor in-seat movement, and will remain under the cushion throughout the study. A mobile app associated with the WiSAT mat may also be installed on participants phone, or provided with a separate mobile device. This app will remain in the background and be used to maintain the clock on the WiSAT data logger. Users may open the app to determine if the WiSAT device needs to be charged, but the app will not provide any weight-shift feedback or information. The participant will perform three leans to initialize the WiSAT mat and ensure accurate monitoring,

Baseline Collection: During the 2-week baseline collection, the in-seat movement behavior will be continuously and passively (no interaction required by the participant) measured with the WiSAT mat installed underneath the wheelchair cushion to determine how much movement the participant performs.

Pre-Intervention Phase Calls/Visits: Before each intervention phase, study staff will meet with the participant via phone, video call, or in-person to assist the participant in setting up the correct system for the phase. Study staff will help the participant download the correct mobile app onto their phone. They will be instructed on how to properly fit and secure the correct system to their wheelchair cushion. Participants will be directed to set personal weight-shifting goals within the app that will generate customized weight-shift reminders (or to leave the default setting). Questions regarding use of the intervention will be answered at this time, skin/general health may be assessed, and the WiSAT leans will be performed again. There will be two pre-intervention calls/visits at beginning of weeks 3 and 9.

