Intervention Phases: During the intervention phases, the participants will have full access to their designated system (Sensoria® Mat or AW-Shift©) and data from their interactions with each system will be recorded remotely. No PHI is collected through either system. Participants may be asked to perform regular tasks or weight-shifts throughout the intervention phases. Study staff will be able to see the participant's interactions with the systems and may contact them during this time regarding technical difficulties.

Post-Intervention Phase Calls/Visits: Immediately after each intervention phase, study staff (who are not masked to the participant IDs) will meet with the participant via phone, video call, or in-person to check-in on their skin/general health, and prepare them for the washout phase. They will complete questionnaires by phone,

electronically/via email (REDCap), or they may be mailed a hard copy. There will be two post-intervention calls/visits at the end of weeks 6 and 12.

At the 2nd post-intervention call/visit, the participant will be instructed on how to return the study equipment and study apps will be deactivated/removed from their phone.

Washout Phase: The Sensoria® Mat and AW-Shift© apps are deactivated during the washout phase. The WiSAT mat will continue to passively monitor in-seat movement, and the system used in Intervention Phase 1 will be removed from their wheelchair.

Study Timeline:

	Screening Call	Informed Consent	Baseline Visit	Baseline Collection (2 weeks)	Intervention Phase 1		Washout Phase (2 weeks)	Intervention Phase 2	
					Pre-Intervention Call/Visit	Post-Intervention Call/Visit		Pre-Intervention Call/Visit	Post-Intervention Call/Visit
Visit No.	0	1		2	3		4	5	
Visit Week	-2	0		3	6		9	12	
Allowable window (in days)		±7		±1	±1		±1	±1	
Inclusion/Exclusion	X	X							
Informed Consent*		X*	X*						
Demographics/SCI and Medical History			X+						
Skin/Health Check	X	X+		X	X		X	X	
Pressure Injury/Weight-Shift Guidelines		X							
WiSAT System Installation		X							
Leans for WiSAT Initialization		X		X			X	X	
System Training/Set-Up		X		X				X	
PUK Questionnaire		X+							
SE Questionnaire		X+			X				X
Early Detection and Action: Pressure-Related Concerns Questionnaire			X+		X				X
SUS Questionnaire					X				X
Usability Questions					X				X
Structured Interview Questions					X				X
Return Equipment					X				X

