Change in in-seat movement between baseline and intervention: The difference in average weight-shift frequencies per hour of wheelchair occupancy between the baseline phase and the intervention phases will be calculated to determine if having an intervention increased in-seat movement. Weight-shifts will be measured by the WiSAT mat, where a weight-shift is defined as a partial unloading lasting more than 15 seconds, and a pressure relief is a specific weight-shift that completely unloads the buttocks for more than 15 seconds. The number of weight-shifts is calculated for each day as the number of events divided by the number of hours spent in the wheelchair. The daily values are averaged across days with at least 4 hours of wheelchair occupancy to define the value for the study phase.

Secondary Outcome Measures:

Self-efficacy: A self-efficacy for weight-shift performance scale is being developed and psychometrically tested as part of related study at Mayo Clinic. Development of this scale follows Albert Bandura's guidelines for creating self-efficacy scales [84]. Items are self-scored by the participant on a scale of 0-100. Item analysis will allow comparison of the different compensatory techniques across the various sub-tasks related to shifting weight or moving more frequently. This level of analysis may allow clinicians to eventually screen individuals for specific challenges and, based on areas where self-efficacy is low, recommend the most appropriate type of compensatory strategy. Self-efficacy is assessed during the baseline visit, during each post-intervention video call, and during the follow-up visit.

Comparison of systems: The difference in average weight-shift and pressure relief frequencies per hour of wheelchair occupancy between the baseline phase and the intervention phases will be calculated and compared across the systems to determine whether there is a difference across systems' effectiveness.

Change in consistency/distribution of weight-shifts: Consistency of weight-shifts is measured by two metrics of the distribution of weight-shifts across a day: 1) The longest daily duration the participant is seated without performing a weight-shift, and 2) The coefficient of variation of the time between weight-shifts. An effective system will reduce the longest daily duration without a weight-shift, and may reduce the coefficient of variation of time between weight-shifts.

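### With three scheduled self-efficacy readings, the SA3b time-trend model does not estimate the change from baseline: a steady rise is estimated as zero, unless an off-system reading exists

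*Combined protocol and SAP*

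**What the plan says.** The Data Analysis Plan (SA3b Hypothesis) tests whether "Self-efficacy beliefs for completing weight-shifts will increase with use of the feedback systems". The method is one sentence: "The change in self-efficacy will be analyzed using a mixed effect model as described in SA3a Hyp". The SA3a paragraph defines that model as a "mixed effect model with fixed effects for treatment and time trend, and mixed effects for subject and time trend within subject". Under Endpoints, the secondary endpoint is how far self-efficacy moves from baseline to the interventions.

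The documents give two accounts of when self-efficacy is measured:

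- **Study Timeline table.** The row "SE Questionnaire" is marked at baseline and at the two post-intervention contacts only. On the timing of those contacts: "There will be two post-intervention calls/visits at the end of weeks 6 and 12".
- **Secondary Outcome Measures, Self-efficacy.** "Self-efficacy is assessed during the baseline visit, during each post-intervention video call, and during the follow-up visit". The timeline contains no follow-up visit.

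On scoring: "Items are self-scored by the participant on a scale of 0-100". No SD and no power figure are given for self-efficacy.

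**The concern.** The SA3a model was written for movement, which the WiSAT mat records throughout baseline, both interventions and washout. Movement therefore has off-system data after the first system, which helps to separate a system effect from a time trend. On the timeline, self-efficacy has one reading before any system and two readings on a system, with none off-system in between or afterwards. A treatment effect and a time trend must then be separated from three points per person.

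The hypothesis is that self-efficacy increases with use. If it keeps increasing through the second phase, that is the pattern a linear trend absorbs. Carried out as written, the analysis could report no effect, or a negative one, while mean scores rise in every phase.

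**Working it through.** **1. The plan's own figures.** The only stated figures concern movement (Power Statement and Table 1).
- Attrition: 48 / (1 − 0.20) = 60, as stated.
- Power: I used a linear trend with the stated SDs (error 0.35, subject 0.8, time within subject 0.2) and assumed phase midpoints at weeks 1, 4 and 10, with time in 6-week units. At n = 48, power for a 50% increase is 98% (stated 97%), and for a 25% increase 59% (stated 55%).
- For 25% versus 50% between systems, the results at n = 48, 54 and 60 are 67/72/77% (stated 67/71/78%).
- Three-phase models without a trend give 77–88% for a 25% increase at n = 48, well above the stated 55%.

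Table 1 therefore fits a linear trend better than no trend. This depends on the assumed spacing: equally spaced phases give 41% and 88% for 25% and 50% increases. A single SD for the time-within-subject effect also points to a slope. The plan never uses the word linear.

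**2. What the model estimates.** Take readings at weeks 0, 6 and 12, two balanced sequences, and all participants completing both systems. The mean system effect is 2·y6 − y0 − y12.

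| Scores at weeks 0, 6, 12 | With trend | Mean post minus baseline |
|---|---|---|
| 60, 70, 80 | 140 − 60 − 80 = 0 | 75 − 60 = 15 |
| 60, 70, 85 | 140 − 60 − 85 = −5 | 77.5 − 60 = 17.5 |
| 60, 70, 75 | 140 − 60 − 75 = 5 | 72.5 − 60 = 12.5 |
| 60, 70, 70 | 140 − 60 − 70 = 10 | 70 − 60 = 10 |

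**3. Precision.** Units are residual SD/√n, with no slope variance. Let m be 1 on a system and 0 off it. The variance of the mean effect is 1 / (S_mm − S_mt²/S_tt), where each S is a centred sum over the readings. Each system against baseline adds a quarter of the between-system variance: 2/4 = 0.5.
- With trend: S_mm = 2/3, S_mt = 6, S_tt = 72. Variance of the mean = 1 / (2/3 − 36/72) = 6, so SE 2.45. Per system 6 + 0.5 = 6.5, so SE 2.55.
- Without trend: 1 / (2/3) = 1.5, so SE 1.22. Per system 1.5 + 0.5 = 2, so SE 1.41.
- Ratios: 2.55/1.41 = 1.80 per system and 2.45/1.22 = 2.00 for the mean.
- At n = 48 the per-system SEs are 0.368 and 0.204 residual SD. The effect detectable with 80% power is (1.96 + 0.8416) × SE, which is 1.03 against 0.57.
- Keeping a random slope at the movement ratio (0.2/0.35) and dropping only the fixed trend gives 0.369/0.236 = 1.56 per system and 1.68 for the mean. The penalty thus comes from the fixed trend.
- Between systems the ratio is 1.00.

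**4. Abbreviated participants.** Study Design allows up to 20 per site to complete one intervention. With 40 of 60 abbreviated, the steady rise is still estimated as 0, and the SE ratio is 1.84–1.89.

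**5. If an off-system reading exists.** Code it as m = 0 and apply the same formula; S_mm is now 1.
- Follow-up at week 13 (assumed): S_mt = 2.5, S_tt = 108.75. Variance 1 / (1 − 6.25/108.75) = 1.06. Per-system SE √1.56 = 1.25, against √1.5 = 1.22 without trend.
- The week-9 call: S_mt = 4.5, S_tt = 78.75. Variance 1 / (1 − 20.25/78.75) = 1.35. Per-system SE √1.85 = 1.36. Counting the start of week 9 as 8 elapsed weeks gives S_mt = 5, S_tt = 75, variance 1.5 and SE √2 = 1.41.
- With a week-13 reading, the steady rise is estimated as 1.1 if the score stays at 80 and 14.3 if it returns to 60.

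**The case against.** **Adjusting for a trend is defensible.** Every participant uses a system and every on-system reading follows baseline. A constant rise over 12 weeks, which include two weeks of baseline collection and two of washout, cannot be told apart from drift or retest effects. A gain that appears and is then held is recovered without bias. This stands: the trend model is a reasonable conservative check. It does not stand as the only analysis, because the endpoint is the change from baseline and the model estimates something else.

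**The result depends on disputed readings and an unstated form of trend.** This also stands. A real follow-up reading off the system would remove most of the SE penalty. Phases may be paused, so the exact weights hold only under nominal timing or visit-number coding. A free three-level time factor would not help, because it would alias the mean system effect with time completely.

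**Stronger readings that a reader might infer.**
- That self-efficacy precision is always nearly halved, so that 48 people count as about 15 (48 × 2/6.5 = 14.8). That figure takes the timeline as right and slope variance as zero. At the movement ratio it is about 20 (48/1.56² = 19.7).
- That the random slope causes the loss. It does not; the fixed trend does.
- That the plan's washout adjustment fails for self-efficacy. That sentence concerns movement, and SA3b does not clearly adopt it.
- That any benefit would be missed. The held step shows otherwise.

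**Conclusion.** The point holds conditionally. On the Study Timeline's three readings and a linear trend, the SA3b model estimates 2 × (week 6) − baseline − (week 12), which is not the stated endpoint. A steady rise gives 0 and an accelerating rise gives a negative effect. The SE is 1.80 times larger per system and 2.00 times for the two-system mean, or about 1.56 and 1.68 if a random slope is kept in both models.

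The assumptions are a linear trend (inferred), nominal visit timing and no off-system reading after baseline. The SE ratios do not depend on the unstated self-efficacy SD. The comparison between systems is unaffected. The documents do not support saying that the plan cannot detect a self-efficacy gain, or that the SE penalty applies whichever schedule is followed. The timeline and the outcome text contradict each other on the follow-up reading, and that must be settled first.

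**What to change.** 1. **Reconcile the readings.** Make the Study Timeline and the Self-efficacy paragraph agree on whether a follow-up reading exists, when it is taken, and whether the participant is then off the system.
2. **Give SA3b its own model.**
   - Fixed effects: condition (baseline, after AW-Shift, after Sensoria) and a centred phase contrast coded 0 at baseline, −½ in phase 1 and +½ in phase 2. A three-level period factor is aliased with condition. A 0/1 phase-2 indicator raises the per-system SE to 1.58 and turns the default system average into week 6 minus baseline.
   - A random intercept and no fixed time trend.
   - Robust standard errors, or a check that allows person-specific drift. At the movement ratio, the SE of the before-after mean is √(1.5 + 1.5² × (0.2/0.35)²) = 1.49, not 1.22.
3. **Main contrast.** Mean post-intervention score minus baseline, reported as a before-after change that includes any general drift. Keep the trend-adjusted model as a sensitivity analysis and state how time is coded.
4. **Add the 4-item form at the week-9 contact, before the second system is set up.** The contact is already planned: "There will be two pre-intervention calls/visits at beginning of weeks 3 and 9". This cuts the trend-adjusted per-system SE from 2.55 to about 1.36. It also shows whether gains persist off the system. If they do, coding that reading like baseline pulls the trend-adjusted effect down: with a week-13 reading, 60, 70, 70, 70 gives 3.4.

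**Cost.** SAP wording, one correction to the schedule or outcome text, and four items on an existing call. The downside is that the before-after change cannot be separated from general drift, and the report must say so.
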